1.1 Background

Urticaria, also known as hives, is a common dermatologic condition which presents with the rapid appearance of pale to brightly colored wheals of various sizes ranging from several millimeters to several centimeters, with or without surrounding erythema, pruritus or occasional burning sensations, and the skin returning to normal typically within one to twenty-four hours (1) (2). The pathophysiologic mechanism involves the release of histamine and other mediators from mast cells and basophils; release in the dermis results in urticaria while release in the deeper dermis and subcutaneous tissues results in angioedema (2). Most commonly, symptoms are caused by exposure to allergens, foods, insect venom, medications, and viral infections. Persons of any ages may present with urticaria, with a lifetime prevalence of between 15% and 25% (2) (3)(4).

Acute urticaria is defined as urticaria persisting less than 6 weeks, whereas chronic urticaria persists 6 weeks or longer (2)(5)(6). Second-generation H1 antihistamines are first-line medication for the treatment of acute urticaria. In some cases, they may be titrated to two or even four times the normal dose to control symptoms followed by H2 antihistamines and corticosteroid for severe cases (1)(2). Indication for epinephrine includes emergency treatment of type 1 hypersensitivity reactions (7) and epinephrine injection is recommended in medical prescribing guidelines in the United States (US) for the management of acute flares with associated angioedema in patients with urticaria. Acute urticaria is treated with but often unresponsive to antihistamines and corticosteroids. Intramuscular (IM) epinephrine is typically efficacious in alleviating urticarial flares.

Epinephrine, illustrated in Figure 1 below, is a sympathomimetic catecholamine. Chemically, epinephrine is B-(3, 4dihydroxyphenyl)-a-methyl-aminoethanol. Epinephrine solution deteriorates rapidly on exposure to air or light, turning pink from oxidation to adrenochrome and brown from the formation of melanin. It is a colorless to light yellow crystalline compound, insoluble in water. The formula is $C_9H_{13}NO_3$ and the molecular weight is 183.20442.

Figure 1: Epinephrine

ARS Pharmaceuticals, Inc. (ARS) is investigating an epinephrine nasal spray (ARS-1) for patients with urticaria as a needleless alternative route of epinephrine administration for the treatment of urticarial flares.

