2.0 STUDY OBJECTIVES

2.1 Study Objectives

IM epinephrine injection is indicated in the emergency treatment of allergic reactions (Type I) including anaphylaxis. Both IM and SC dosing of epinephrine is approved by the FDA as efficacious in product labeling in the US. Epinephrine injection is also recommended in medical prescribing guidelines in the US for the management of acute flares with associated angioedema in patients with urticaria. Acute urticaria is typically treated with but often unresponsive to antihistamines and corticosteroids. IM epinephrine is typically efficacious in alleviating urticarial flares. An epinephrine nasal spray (ARS-1) is being developed for patients as a needleless alternative route of epinephrine administration for the treatment of acute urticaria.

| Objective | Endpoints |
|--|--|
| Primary | |
| 
To determine the effect of ARS-1 versus placebo based on a patient reported pruritus/hive score
 
To assess time to effect and duration of effect on acute flares associated with urticaria based on a patient reported pruritus/hive score.
 | 
 • A patient reported pruritus/hive score • Patient reported pain associated with the urticaria flair based on visual analog scale (VAS) • An investigator-rated extent of urticaria; % of body area with urticaria • An investigator-rated erythema score |
| Secondary | |
| To assess the safety and tolerability of ARS-1 in subjects with urticaria after IN administration of epinephrine. | 
 • AEs • Vital signs |
| [REDACTED] | |
| [REDACTED] | |

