3.3 Efficacy Assessments

The following efficacy assessments will be evaluated based on self-reported and clinical assessments of pruritus at pre-dose, and at 5 (± 2 min), 10 (± 2 min), 15 (± 3 min), 30 (± 5 min), 45 (± 5 min), 60 (± 10 min), 120 (± 10 min) minutes, and every 60 minutes (± 10 min) after dosing until the discharge criteria (the time when symptoms of acute urticaria have been effectively treated based on the investigator's or his/her designee's opinion will be recorded, not necessarily when subjects discharged) is met for acute flare and until urticaria symptoms returns to the baseline for chronic spontaneous urticaria. If the time to return to baseline for chronic spontaneous urticaria is beyond 4 hours, such time may be recorded by the patient and reported in the follow-up call. The actual time of the assessment and of when the symptoms return to the baseline will be recorded. Subjects should also record the date and time of recurrence, if any, of symptoms after they leave the clinic.

- A patient reported pruritus/hive score from 0 (none) to 3 (severe) for itch and hive using Uniform Assessment System (UAS) twice daily as below:

| Itch Severity Score | Amount of Itch | Itch Severity at Each Assessment |
|---------------------|----------------|--|
| 0 | None | None |
| 1 | Mild | Minimal awareness, easily tolerated |
| 2 | Moderate | Definite awareness, bothersome but tolerable |
| 3 | Intense | Difficult to tolerate |

| Hive Severity Score | Number of Hives at Each Assessment |
|---------------------|------------------------------------|
| 0 | None |
| 1 | 1-6 |
| 2 | 7-12 |
| 3 | >12 |

- Patient reported pain associated with the urticaria flare will be recorded based on a self-reported VAS score

- An investigator-rated extent of urticaria; % of body area with urticaria (Grade 1: urticarial lesions covering < 10% body surface area [BSA]; Grade 2: urticarial lesions covering 10-30% BSA; Grade 3: urticarial lesions covering > 30% BSA)
- An investigator-rated erythema score (0 = none, 1 = almost clear [slight redness], 2 = mild erythema [definite redness], 3 = moderate erythema [marked redness], 4 = severe erythema [fiery redness])

[REDACTED]

[REDACTED]

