4.1 Inclusion Criteria

For a subject to be eligible for this study, he or she must meet **all** of the following criteria:

1. Is a male or female subject between the ages of 18 and 65 years, inclusive.
2. Has been clinically diagnosed with acute flares or with chronic spontaneous urticaria with unknown etiology and have urticaria symptom (patient-rated pruritus and hive severity score ≥ 2) at least two (2) times a week while on a chronic treatment (e.g., antihistamine) at least 2 weeks before dosing and will remain the same throughout the study.
3. Has body weight more than 30 kg and body mass index between 18 and 34 kg/m², inclusive.
4. Has no medical history of hypertension and cardiovascular disease in the last 10 years. Controlled hypertension without beta blocker confirmed by the Investigator is acceptable.
5. At screening, has stable vital signs in the following ranges (after 5 minutes of rest):
 - SBP ≥ 90 and ≤ 140 mmHg
 - DBP ≥ 50 and ≤ 90 mmHg
 - HR ≥ 45 and ≤ 100 bpm

Note: Each BP should be taken after at least 5 minutes rest in a chair with back supported, legs uncrossed, and upper arm bared (slight recline for comfort is permitted). If vital signs are out of range, the Investigator may obtain two additional readings, so that up to 3 consecutive assessments are made within 1 hour.

6. If female, is not pregnant or breastfeeding based on the following:
 - a. agree to the use of highly effective contraceptive methods for at least 2 weeks before baseline until 7 days after the last day of study drug and a negative urine pregnancy test at screening; or
 - b. is of nonchildbearing potential defined as clinically infertile as the result of surgical sterilization (hysterectomy, bilateral tubal ligation, bilateral salpingectomy and/or bilateral oophorectomy); or

- c. is confirmed postmenopausal status (defined as either having amenorrhea for ≥ 12 consecutive months without another cause and documented serum follicle-stimulating hormone (FSH) level > 40 mIU/mL or another documented medical condition (e.g., was born without a uterus)).

NOTE: The following are considered highly effective contraceptive methods: abstinence, hormonal oral contraceptives, injectables, and patches; intrauterine devices; double-barrier methods (synthetic condom, diaphragm, or cervical cap used with spermicidal foam, cream, or gel); Nexplanon contraceptive implant (if implanted within 3 years); and male partner sterilization.

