6.0 EFFICACY

Efficacy assessments will be evaluated based on self-reported and clinical assessments of pruritus at pre-dose, and at 5 (\pm 2 min), 10 (\pm 2 min), 15 (\pm 3 min), 30 (\pm 5 min), 45 (\pm 5 min), 60 (\pm 10 min), 120 (\pm 10 min) minutes, and every 60 minutes (\pm 10 min) after dosing until the discharge criteria (the time when symptoms of acute urticaria have been effectively treated based on the Investigator's or his/her designee's opinion will be recorded, not necessarily when

subjects discharged) is met for acute flare and until urticaria symptoms returns to the baseline for chronic spontaneous urticaria. If the time to return to baseline for chronic spontaneous urticaria is beyond 4 hours, such time may be recorded by the patient and reported in the follow-up call. The actual time of the assessment and of when the symptoms return to the baseline will be recorded. Subjects should also report the date and time of recurrence, if any, of symptoms after they leave the clinic.

The following efficacy assessments will be evaluated:

- A patient reported pruritus/hive score from 0 (none) to 3 (severe) for itch and hive using UAS twice daily as below:

| Itch Severity Score | Amount of Itch | Itch Severity at Each Assessment |
|---------------------|----------------|--|
| 0 | None | None |
| 1 | Mild | Minimal awareness, easily tolerated |
| 2 | Moderate | Definite awareness, bothersome but tolerable |
| 3 | Intense | Difficult to tolerate |

| Hive Severity Score | Number of Hives at Each Assessment |
|---------------------|------------------------------------|
| 0 | None |
| 1 | 1-6 |
| 2 | 7-12 |
| 3 | >12 |

- Patient reported pain associated with the urticaria flare will be recorded based on a self-reported VAS score,
- An investigator-rated extent of urticaria; % of body area with urticaria (Grade 1: urticarial lesions covering < 10% BSA; Grade 2: urticarial lesions covering 10-30% BSA; Grade 3: urticarial lesions covering > 30% BSA),
- An investigator-rated erythema score (0 = none, 1 = almost clear [slight redness], 2 = mild erythema [definite redness], 3 = moderate erythema [marked redness], 4 = severe erythema [fiery redness]).

[REDACTED]

[REDACTED]

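### The investigator-rated extent scale has no grade for clear skin, so a flare that starts in its lowest grade shows no change even if it clears completely

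*Combined protocol and SAP*

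**What the plan says.** Section 2.1 lists "An investigator-rated extent of urticaria; % of body area with urticaria" among the endpoints for the primary objectives. The synopsis, section 3.3 and section 6.0 each set out how it is scored, and all three give the same three grades. Section 3.3 has "An investigator-rated extent of urticaria; % of body area with urticaria (Grade 1: urticarial lesions covering < 10% body surface area [BSA" followed by "Grade 2: urticarial lesions covering 10-30% BSA; Grade 3: urticarial lesions covering > 30% BSA". Section 6.0 repeats it: "of body area with urticaria (Grade 1: urticarial lesions covering < 10% BSA; Grade 2: urticarial lesions covering 10-30% BSA". None of the three includes a grade for no lesions.

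The other scales in section 3.3 do have a zero. Itch and hive scores both run from 0 (none) to 3, and the companion investigator scale is "An investigator-rated erythema score (0 = none, 1 = almost clear [slight redness" and so on up to 4.

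Other relevant text:
- Section 4.1 requires that subjects "have urticaria symptom (patient-rated pruritus and hive severity score ≥ 2) at least two (2) times a week while on a chronic treatment". The hive table in section 3.3 sets score 2 at 7-12 hives and score 3 at more than 12, with no upper limit.
- Section 1.1 describes "wheals of various sizes ranging from several millimeters to several centimeters".
- Section 14.3.1 takes the pre-dose value at each visit as baseline and defines time to effect as the time to fall by one, two and three grades.

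**The concern.** On a scale whose lowest level is under 10% of body surface, a flare with few or small wheals is already at the bottom before dosing. Complete clearing and no response then receive the same grade, and the only movement the scale can record is worsening. The entry criterion makes this relevant, because the hive count it points to appears to cover far less than 10% of the body.

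Flares at the floor contribute no information on improvement, whichever treatment was given. That dilutes any ARS-1 versus placebo difference in extent, and a null result on this endpoint would be hard to interpret. The loss cannot be repaired later, because a grade cannot be turned back into a percentage once the data are collected.

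**Working it through.** The plan gives no effect size, power or expected BSA for this endpoint, so there is no figure to reproduce. The check is geometric.

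**Inputs from the documents**
- Hive score 2 = 7-12 hives (section 3.3).
- Wheal size from several millimetres to several centimetres (section 1.1).
- Grade 1 ends at 10% BSA (section 3.3).

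**Assumptions (not in the documents)**
- Total body surface 1.8 m² = 18,000 cm², with a range of 1.5 to 2.2 m². An extreme of 0.9 m² is near the smallest body size that the weight and BMI limits of section 4.1 allow.
- Circular wheals that do not overlap, diameter d of 1 to 10 cm.

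**Formula**

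Percent BSA = n × π × d² / 4 ÷ (total BSA in cm²) × 100

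**Results at 1.8 m²**

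| Diameter | Area of one wheal (cm²) | 7 hives | 12 hives | Hives needed for 10% (1,800 cm²) |
|---|---|---|---|---|
| 1 cm | 0.785 | 0.03% | 0.05% | 2,292 |
| 3 cm | 7.07 | 0.27% | 0.47% | 255 |
| 5 cm | 19.6 | 0.76% | 1.31% | 92 |
| 10 cm | 78.5 | 3.05% | 5.24% | 23 |

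Example: 12 × 19.6 = 236 cm², and 236 / 18,000 = 1.3%.

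**Diameter needed to leave Grade 1 at 1.8 m²**

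d = √(4 × 1,800 / (n × π)), which is 13.8 cm for 12 hives and 18.1 cm for 7.

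**Sensitivity to body size**

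Twelve wheals of 5 cm cover 1.6% at 1.5 m², 1.1% at 2.2 m² and 2.6% at 0.9 m². Over all these body sizes and diameters, the only case above 10% is 12 wheals of 10 cm on 0.9 m² (942 / 9,000 = 10.5%). A flare at hive score 2 therefore starts in Grade 1 under essentially any plausible input.

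**What the scale can register**

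| Pre-dose grade | Largest fall, printed scale | Largest fall if Grade 0 is added |
|---|---|---|
| 1 | 0 | 1 |
| 2 | 1 | 2 |
| 3 | 2 | 3 |

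If the time-to-effect definition of section 14.3.1 is applied to this scale, no fall can occur from Grade 1 and a three-grade fall is impossible for anyone.

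**Size of the loss**

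Let f be the share of flares that start in Grade 1. These contribute zero, so the mean achievable fall is (1 − f) times the mean among flares that start higher. With 32 subjects in a treatment period, the number able to show any fall is 32 × (1 − f): 16 for f = 0.50, 8 for f = 0.75 and about 3 for f = 0.90. The documents do not give f; these values only show the range.

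**The case against.** The other side has five arguments.

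1. **The percentage may be collected anyway.** The endpoint name refers to a percentage of body area, and the synopsis analyses quantitative endpoints by linear mixed model. If raw percentages are recorded and analysed, the floor disappears. Text next to this item in sections 3.3 and 6.0, and section 14.5, is blacked out, and the eCRF is not available. This is a genuine uncertainty, but the visible text defines only grades, in three places. The name alone does not cure the floor.

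2. **Clear skin may not be scored Grade 1.** The grade wording presupposes lesions, and the adverse event severity scale (Table 8) also starts at 1 and leaves absence ungraded. That is a fair reading. It means the coding of clear skin is unspecified, which still gives a cleared flare no defined lower value.

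3. **The population may be more extensive than hive score 2.** The entry score is a minimum, is not required at the treated flare, and may be per item or combined. Hive score 3 has no upper limit. Numerous, large or confluent wheals could pass 10%, and the protocol does not say whether surrounding redness counts as covered area. This stands: the documents give no baseline distribution, so a reader who infers that most flares, or the typical subject, start in Grade 1 goes beyond them. If the entry score is a combined one, fewer hives qualify and the floor is more pronounced.

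4. **Clearing is measured elsewhere.** Hive, itch and erythema scores, each with a zero, are taken at the same times. Both efficacy objectives rest on the pruritus/hive score, and the synopsis declares all analyses exploratory. This stands and limits the harm.

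5. **Return to baseline.** A reader might infer that a Grade 1 flare meets this criterion at every assessment. The documents do not support that. They tie return to baseline to urticaria symptoms without naming the extent scale, and a Grade 1 flare can still worsen to a higher grade.

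**Conclusion.** The point holds as a floor effect. The printed extent scale has no grade for clear skin. A flare of 7-12 hives covers about 0.03% to 5% of an assumed 1.8 m² for wheals of 1 to 10 cm, so it starts in Grade 1 and can show no grade change on clearing. This rests on separate circular wheals and on the grades being what is recorded and analysed.

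A reader might infer that the endpoint cannot show improvement at all. The documents do not support that: flares starting in Grade 2 can fall one grade and those in Grade 3 can fall two. Nor would the trial be blind to clearing, since three other scores capture it. What is lost is sensitivity on one endpoint in the primary block, by an amount that depends on an unknown share of flares. The change is worth making because it costs almost nothing now and cannot be made after data collection.

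**What to change.** In the synopsis, section 3.3, section 6.0 and the eCRF, record the estimated percent BSA as a number at every assessment, with 0 for no lesions, and analyse its change from pre-dose. If grades are kept, add Grade 0 = no urticarial lesions and derive all grades from the recorded percentage. In section 14.3.1, say whether the one-, two- and three-grade definition of time to effect applies to extent, so that it matches the number of levels on the scale.

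The cost is one eCRF field and a few lines of text. The same investigator makes the same inspection at the same times. The small downside is rater variability in low percentages. The change has to be in place before the first assessment is recorded.

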3.4 Safety Assessments

Safety assessments include AEs and vital signs.

3.5 Concomitant Medications

3.5.1 Prior and Concomitant Medications

Prior medications are defined as medications that were taken within 30 days prior to initial dosing with study drug.

Concomitant medications are defined as medications taken any time after the start of dosing until discharge assessments.

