10.5 Discharge Assessments (Treatment Periods 1 - 3)

Discharge assessments will be completed by the Investigator or his/her designee once symptoms of urticaria have been effectively treated for an acute flare or returned to baseline for chronic spontaneous urticaria. Actual time by hours and minutes will be recorded. In addition, AEs and concomitant medication will also be recorded.

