Appendix A: Schedule of Study Procedures

Table 1: Schedule of Study Procedures

| Study Procedure Study Day | Screening Day -90 to -1 | Treatment Period 1 | | Treatment Period 2 | | Treatment Period 3 | |
|--|----------------------------|-----------------------|-----------|-----------------------|-----------|-----------------------|-----------|
| | | pre-dose | post-dose | pre-dose | post-dose | pre-dose | post-dose |
| Signed informed consent | X | | | | | | |
| Inclusion/Exclusion Criteria | X | X | | | | | |
| Admission to Clinical Site | | X | | X | | X | |
| Medical history | X | X | | | | | |
| Complete or targeted physical exam | X | X | | X | | X | |
| Vital signs ^a | X | X | X | X | X | X | X |
| Height and Weight | X | | | | | | |
| Hematology, Serum Chemistry, Coagulation, and Urinalysis | X | | | | | | |
| HIV Antibody and Hepatitis Tests | X | | | | | | |
| Urine Drug and Cotinine, Saliva/Urine Alcohol Screen | X | | | | | | |
| Prior and Concomitant medication assessment | X | X | X | X | X | X | X |
| Urine pregnancy test ^b | X | | | | | | |
| Adverse event assessment ^c | | | X | X | X | X | X |
| ECG (12-Lead in triplicate) ^d | X | | | | | | |
| Study Medication | | | X | | X | | X |
| Patient reported pruritus/hive score and VAS for pain ^e | | X | X | X | X | X | X |
| Investigator-rated extent of urticaria and erythema score ^f | | X | X | X | X | X | X |
| | | | | | | | |
| | | | | | | | |
| | | | | | | | |
| Discharge assessment ^d | | | X | | X | | X |
| | | | | | | | |

- Vital signs (BP, PR, temperature, and respiratory rate) will be taken at pre-dose, and at 5 (\pm 2 min), 20 (\pm 2 min), 30 (\pm 2 min), 60 (\pm 5 min), and 120 (\pm 5 min) minutes after dosing. Actual times by hour/minutes/seconds will be recorded.
- A urine pregnancy test will be administered to females of childbearing potential at screening.
- AE assessment will begin after dosing and continue until discharge. AEs will also be solicited at the follow up telephone call.
- ECG is to be performed in triplicate.

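### Concomitant medication is collected only to discharge, while late return-to-baseline times and all recurrence times come from home, and no readable rule covers acute medication taken in between

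*Combined protocol and SAP*

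**What the plan says.** Section 3.5.1 sets the window: "Concomitant medications are defined as medications taken any time after the start of dosing until discharge assessments". Section 10.5, on the discharge assessment in each of the three periods, is consistent with it: "In addition, AEs and concomitant medication will also be recorded".

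Two kinds of outcome data continue after discharge. Section 3.3 says "If the time to return to baseline for chronic spontaneous urticaria is beyond 4 hours, such time may be recorded by the patient", with the time passed on at the follow-up call. For everyone it adds: "Subjects should also record the date and time of recurrence, if any, of symptoms after they leave the clinic". Section 6.0 repeats both arrangements.

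Duration is a stated primary aim in Section 2.1: "To assess time to effect and duration of effect on acute flares associated with urticaria based on a patient reported pruritus/hive score". Section 14.3.1 defines duration by grade relative to the pre-dose value. Its readable text says nothing about medication taken before the end point is reached.

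On the follow-up call, the readable text gives the late return-to-baseline time and, in an Appendix A note, "AEs will also be solicited at the follow up telephone call". It does not mention medication. Appendix A does mark the row "Prior and Concomitant medication assessment" at screening and before and after dosing in every period, and Section 10.2 lists concomitant medication among the pre-dose items.

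**The concern.** The outcome window is longer than the medication window. A subject with an acute flare may leave from 2 hours after dosing, and a subject with chronic spontaneous urticaria may record a return to baseline beyond 4 hours. Sections 3.1 and 10.2 ask subjects to come in before taking other acute medication, so the protocol expects that they may have some to take. If they take it at home, the recorded return or recurrence time reflects the spray plus that medication.

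At stake is the interpretation of duration and recurrence. If the name and clock time of home medication are not collected when it is taken, they cannot be reliably reconstructed later.

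**Working it through.** The plan gives no figure to reproduce: Section 14.1 rests the sample size on practical grounds, and no readable text assumes a duration or a rate of home medication. The check is therefore mainly documentary.

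**1. The definition.** Section 10.5 places a discharge assessment in each period, so Section 3.5.1 reads most naturally period by period. Medication taken between visits is then not concomitant. It is not prior either, because prior medication is limited to the 30 days before initial dosing. If the definition instead runs from first dose to last discharge, use between periods falls inside it and use after the Period 3 discharge does not. Either way some home use is outside.

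**2. Later checks.** Use after Periods 1 and 2 can be asked about at the next pre-dose visit. No later visit is visible after Period 3. Both sequences in Section 3.1.1 put placebo second and an ARS-1 dose third. With the Synopsis sample size of 32 and full completion:

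- planned sprays: 32 × 3 = 96, of which 64 are ARS-1 and 32 placebo
- ARS-1 sprays with no later visible check: 32 of 64 (50%)
- placebo sprays with no later visible check: 0 of 32

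**3. From detection to bias.** Nothing in the readable analysis plan acts on home medication once it is found. A placebo duration altered by home medication stays altered whether or not the use is recorded, exactly as an ARS-1 duration does. The counts in step 2 describe detection, not a difference in bias.

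**4. Direction.** Section 14.3.1 literally starts duration when the grade rises above baseline and ends it when the grade returns there, with baseline being the pre-dose value. On that wording home medication could shorten the recorded time. It lengthens the time only if duration means time improved relative to pre-dose.

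**5. Illustration of size (every input is an assumption; none is in the documents).** Take duration as time improved. Let r be the share relieved, m the median relief in hours, q the share of those still improved at 4 hours who take home medication, and let each such use add 6 hours.

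Share still improved at 4 h = r × 2^(−4/m). Shift in mean duration = share × q × 6 h.

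- ARS-1, r = 0.70, m = 6: 0.70 × 2^(−4/6) = 0.441
- Placebo, r = 0.30, m = 4: 0.30 × 2^(−1) = 0.150
- At q = 0.30: ARS-1 0.441 × 0.30 × 6 = 0.79 h; placebo 0.150 × 0.30 × 6 = 0.27 h; net 0.52 h

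| Assumed response | Net shift, q = 0.10 | q = 0.30 | q = 0.50 |
|---|---|---|---|
| ARS-1 as above; placebo r = 0 | 0.26 h | 0.79 h | 1.32 h |
| ARS-1 as above; placebo r = 0.30, m = 4 | 0.17 h | 0.52 h | 0.87 h |
| ARS-1 as above; placebo r = 0.50, m = 4 | 0.11 h | 0.34 h | 0.57 h |
| Both r = 0.50, m = 4 | 0 | 0 | 0 |

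The net shift runs from zero to more than an hour depending on response rates that the documents do not give. Placebo escapes it entirely only if no placebo subject improves, and Section 1.1 describes the skin clearing by itself within one to twenty-four hours.

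**6. What is untouched.** Section 3.6 keeps subjects in the clinic for at least 2 hours, so home medication cannot affect the scheduled scores from 5 to 120 minutes.

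**The case against.** The strongest reply is that the gap is narrow and partly controlled. Inclusion criterion 2 requires chronic treatment to stay the same throughout, rescue is recorded at discharge, and the home route into duration is explicit only for chronic spontaneous urticaria beyond 4 hours. No readable text makes time to recurrence an analysed endpoint or feeds it into duration. The Synopsis calls all analyses exploratory. The prohibited-medication text (Section 3.5.2), some post-dose items (Section 10.4), schedule rows and notes in Appendix A, and Section 14.5 are redacted, so the call may cover more than can be seen.

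Much of this stands and limits the point. It does not remove it. Stable chronic treatment does not exclude acute medication after discharge, and rescue recorded at discharge is by definition not later use. The definition in Section 3.5.1 is readable and ends at discharge; if a hidden part of the call collects medication, the two need to be reconciled.

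A reader might go further and infer that ARS-1 duration is overstated relative to placebo, because Period 3 is never placebo. The documents do not support that. The window and the home recording are the same for all three treatments, and no readable rule would correct a placebo duration for home use found at a later visit.

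**Conclusion.** The point holds as a gap in data collection and in the analysis rules. Acute medication taken at home before a late return to baseline or a recurrence can fall outside the definition, and no readable rule says what to do with it. Recorded duration and recurrence can therefore reflect home treatment after any of the three treatments. Detection is uneven: no later check is visible for half the planned ARS-1 sprays, while every placebo spray is followed by one, assuming 32 completers and pre-dose checks that ask about the interval since the last visit. A difference in bias between ARS-1 and placebo is not shown, the direction is unsettled until Section 14.3.1 is corrected, and the size cannot be derived from the documents. The conclusion is limited to the readable text. The change is worth making because it is cheap and the information is lost if it is not collected at the time.

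**What to change.** 1. In Section 3.5.1, define concomitant medication as anything taken from the first dose through the last follow-up call, including between periods. Align Section 10.5 and Appendix A.
2. On the home recurrence record and at the follow-up call, capture the name and clock time of any acute urticaria medication.
3. Correct the duration definition in Section 14.3.1 so that it measures time improved, and say which baseline applies in chronic spontaneous urticaria.
4. State one rule for acute medication taken before return to baseline or recurrence, applied identically to all three treatments. Censoring duration at the first such medication is one option, at least as a sensitivity analysis. It should not be the only analysis without justification, since subjects who medicate may be those whose symptoms are coming back.

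The cost is a reworded definition, one extra field, one question on a call that already takes place, and a few lines of analysis text. Some durations will be censored if that rule is chosen. Clinical management does not change.
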